### *Data collection*

Frailty measures (CFS, 30 seconds sit-stand test, hand grip strength, time-up-and-go test) and functional capacity measures (6MWT distance, calculated peak oxygen uptake, DASI score) will be collected at prehabilitation clinic and upon first and last prehabilitation session. We will also evaluate the dose-response effect of the number of prehabilitation sessions attended. The cause for any premature termination of prehabilitation, for example, change in surgical plan or date, patient non-compliance, or logistic difficulties will also be analysed. Quality of life measurement using EQ-5D and emotional resilience screen using DASS-21 will be done at the first and last prehabilitation session. Nutritional status based on measurement of weight, BMI, muscle mass and percentage body fat will be recorded at the first and last prehabilitation session.

The following demographic data will be collected at baseline including age, gender, body weight, body mass index, ASA-PS, details of surgical procedures, length of hospital and ICU stay, pulmonary complications, discharge destination (home, hospital or nursing aged-care facility) and 30-day mortality from patient's medical record.

Assessment	Baseline	First prehab session	Last prehab session	POMI
Enrolment				
Eligibility screen	X			
Demographic data	X			
Comorbidity data	X			
Primary outcomes				
6MWT	X	X	X	
Secondary outcomes				
DASI	X			
Clinical Frailty Scale	X			

Other frailty measures (Hand grip strength, 30s sit-stand test)		X	X	
DASS-21		X	X	
Nutritional status (muscle mass, % fat, BMI, weight)		X	X	
3-day food record		X	X	
Length of hospital and ICU stay				X
Pulmonary complications				X
30-day mortality				X
DAH 30				X

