## **Materials and Methods**

### *Trial design*

This is a single centered, unblinded, single-arm retrospective study.

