**Prehabilitation clinic**

New preoperative care pathway has been implemented since August 2019. In the new preoperative care pathway (Fig 1), referred patients are screened by anaesthesiologists for inclusion into prehabilitation clinic, with the date of the clinic session at least 5 weeks before the estimated operation date. Eligible patients will have the baseline blood samples taken on the same day of clinic attendance. The blood samples include routine bloods plus the investigations necessary for anaemia screening (ferritin, iron profile, C-reactive protein, vitamin B12 and folate level). Anaemia is defined by the World Health Organization as a circulating haemoglobin concentration below 13g/dL for men and 12g/dL for non-pregnant women. Patients found to have absolute iron deficiency anaemia (ferritin <30mcg/L, or ferritin <100mcg/L with transferrin saturation <20%) will be admitted to day surgery centre on the same day for a single dose of intravenous ferric carboxymaltose (20mg/kg for body weight <50kg, 1000mg for body weight >50kg) at least 3 weeks prior to the estimated operation date. The intravenous iron infusion will be given over 30 minutes under close monitoring. Patients will also be screened for malnutrition in the prehabilitation clinic using the Malnutrition Screening Tool (MST). Patients with MST score of more than one will be referred to dietitians for nutritional prehabilitation. Furthermore, functional capacity and frailty of patients will be assessed using Duke Activity Status Index (DASI) questionnaire, 6-minute walk test (6MWT) and Clinical Frailty Scale (CFS). Patients with DASI score <34 or 6MWT distance <400m will be recruited into the prehabilitation program.

[figure not shown]

Fig 1. Workflow of prehabilitation clinic

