### Exercise prehabilitation

Collaboration was made with the Geriatric Day Hospital (GDH) of the same hospital cluster for the prehabilitation service. The GDH at Shatin provides a seamless one-stop service in medicine and geriatrics, physiotherapy, occupational therapy and dietitians. Patients screened eligible for recruitment are sent to GDH within one week after the prehabilitation clinic attendance for further holistic care and assessments. Patients will undergo a structured preoperative exercise training of 3 or more weeks, depending on the schedule of surgery, to optimize the physical and psychosocial fitness of patients with underlying frailty syndrome before surgery by physiotherapists at GDH. The result of the submaximal exercise test from the 6MWT will be used as an estimation of individual peak oxygen uptake and hence oxygen uptake reserve (VO2R) for exercise prescription. Each patient’s prehabilitation program will be individualized and symptom limited, in which exercise prescription and progression will be based on the results of the exercise test, individual health status, exercise performance and training response. Based on the American College of Sport Medicine guidelines on exercise prescription, the exercise protocol comprise of 75-90min of supervised

exercises at least twice per week (3 times per week for the first 2 weeks). There is a combination of moderate-intensity aerobic exercise and resistance training, with the exercise intensity 3-6 according to the modified Borg Scale. In the aerobic exercise, the patients will be asked to perform treadmill walking, stepping exercises and ergometer for 30min. For the resistance training, patients will be asked to perform 10 repetitions per major muscle group of upper and lower limbs with at least 2 sets, depending on individual tolerance and performance. Home exercise program including stretching, aerobic and resistance training, and breathing exercises will be prescribed to patients with guided videos. Advice on smoking cessation and positive psychology support will be given to patients during the prehabilitation program.

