## *Outcome measures*

### **Primary outcomes**

The primary outcome is the changes in the 6MWT distance and the calculated peak oxygen uptake ( $VO_{2peak}$ ) between baseline and upon completion of prehabilitation program. A dose-response effect on 6MWT distance and calculated  $VO_{2peak}$  with regards to the number of prehabilitation sessions attended will be investigated. The 6MWT evaluates the ability of an individual to maintain a moderate level of physical endurance. Moderate to strong correlations have been found between the 6MWT and  $VO_{2peak}$  obtained with other modes of exercise testing. Participants are instructed to walk back and forth a 30m stretch of hallway for 6min at a pace that would make them tired by the end of the walk. A change in 6MWT distance of 20m was considered meaningful as this is the estimated measurement error in community-dwelling elderly. We will also assess the feasibility of the program by examining the recruitment, attrition and adherence of patients to the prehabilitation sessions. The reasons for drop-out from prehabilitation will be recorded.

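### The single-arm primary 6MWT change, if measured from the clinic walk, includes any shift before supervised training, and the plan gives the first-session walk no role in separating the two

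*Combined protocol and SAP*

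**What the plan says.** The Trial design section is explicit: "This is a single centered, unblinded, single-arm retrospective study". There is no concurrent comparison group.

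Under Data collection, the functional capacity measures, among them 6MWT distance and calculated peak oxygen uptake, "will be collected at prehabilitation clinic and upon first and last prehabilitation session". The assessment table agrees for the 6MWT, with marks under three separate columns: baseline, first session and last session.

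Under Primary outcomes, the changes in 6MWT distance and in calculated peak oxygen uptake are taken "between baseline and upon completion of prehabilitation program". That uses two of the three walks. The section on sample size and statistical analysis names Student's t, Mann-Whitney U and chi-square tests. It describes no repeated-measures analysis and gives the remaining walk no use. No section mentions a practice walk or an allowance for repeat testing.

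Three other statements bear on the first interval:

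- Exercise prehabilitation: eligible patients are "sent to GDH within one week after the prehabilitation clinic attendance", and supervised training takes place there.
- Prehabilitation clinic: "Patients with DASI score <34 or 6MWT distance <400m will be recruited into the prehabilitation program". For some patients the clinic walk is therefore also a selection test.
- Prehabilitation clinic: patients with absolute iron deficiency anaemia "will be admitted to day surgery centre on the same day for a single dose of intravenous ferric carboxymaltose".

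**The concern.** With one arm, the primary change is the whole of the evidence on fitness. If it starts at the clinic walk, it covers two different periods: a short one before supervised training, and the training period itself. A change in the first period is not a training effect, whatever its cause, yet it is added to the result. The calculated peak oxygen uptake is derived from the 6MWT, so it carries the same shift.

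The schedule already places a walk at the boundary between the two periods. Reporting the periods separately would show how much of the total change arose before training. This is the only within-study information of that kind on the primary outcome, and the plan does not use it. The 20 m threshold for a meaningful change does not settle the matter, because the plan justifies that figure as measurement error.

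**Working it through.** **The plan's own figure.** Inputs from the sample size section: changes of +25.2 m (SD 50.2) and −16.4 m (SD 46.0), two-sided 0.05, 80% power.

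- Pooled SD = √((50.2² + 46.0²)/2) = 48.15 m.
- Effect size = (25.2 + 16.4)/48.15 = 0.864, which matches the stated 0.86.
- Exact two-sample t test at 0.86: 22 per arm gives 79.6% power and 23 per arm gives 81.4%.

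So 46 reproduces as the total of two arms of 23. This study has no second arm. For a within-patient change of 25.2 m with SD 50.2 m, a paired t test needs 34 patients for 80% power, and 46 give 91%.

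**Effect of a shift before training.** Let L be the mean shift between the clinic walk and the first-session walk. The documents give no value, so L is assumed over 0 to 20 m, the top being the plan's own meaningful change. Other inputs: 46 complete pairs, SD of change 50.2 m, paired t test.

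- Standard error = 50.2/√46 = 50.2/6.78 = 7.40 m; critical t on 45 df = 2.014.
- Chance of significance with no programme effect = P(|T| > 2.014), where T is noncentral t on 45 df with noncentrality L/7.40.

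The last three columns suppose instead that the total gain is 25.2 m and includes L, with SD 50.2 m also applying to the first-to-last change.

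| L (m) | L/7.40 | Significant with no programme effect | Remaining gain (m) | Power at 46 | N for 80% power |
|---|---|---|---|---|---|
| 0 | 0 | 5% | 25.2 | 91% | 34 |
| 5 | 0.68 | 10% | 20.2 | 76% | 51 |
| 10 | 1.35 | 26% | 15.2 | 52% | 88 |
| 15 | 2.03 | 51% | 10.2 | 27% | 193 |
| 20 | 2.70 | 75% | 5.2 | 11% | 734 |

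**Can a shift arise without learning?** As an illustration of regression to the mean, suppose all patients are selected on a first walk below 400 m, from a population with mean 350 to 400 m, SD 90 m and test-retest reliability 0.85 to 0.95 (all assumed). Simulation gives an apparent gain of about 2 to 11 m at the second walk, with no learning and no treatment. Patients who enter on DASI alone are not selected on the walk, so the effect in the actual cohort would be smaller.

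**Precision of the early change.** The half-width of the 95% CI is 2.014 × SD/√46. For an assumed SD of the short-interval difference between 20 and 50.2 m, this runs from 5.9 to 14.9 m.

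**The case against.** *Baseline is not defined.* The assessment table points to the clinic, but the Emotional resilience section calls DASS-21 a baseline measure while the table places it only at the first and last sessions. If baseline for the 6MWT means the first session, the clinic walk already acts as a familiarisation walk and the early shift is not in the primary change. This stands, and it is why the definition comes first in the fix.

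*The early interval does not isolate learning.* A reader might infer that clinic-to-first-session change measures test familiarity. The documents do not support that. The interval also contains regression to the mean and same-day iron in some patients. It misses any learning between the second and third walks. The order of walk and exercise at the first session is unstated, and the text dates the referral to the day hospital, not the first training session. Nothing in the documents describes a different corridor or tester.

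*Subtraction.* A reader might go further and subtract the early change from the later one. First-to-last change already excludes the first familiarity gain, so subtraction would remove it twice. The contrast is walk 3 − 2 × walk 2 + walk 1. With equal independent errors its variance is 6σ² against 2σ² for a single difference, so its SD is √3 times larger. At a single-difference SD of 50.2 m that is 87 m, a half-width of about 26 m, wider than the 25.2 m expected. A rule that similar gains in both intervals mean no programme effect also fails: it has no margin, and it compares roughly a week with three or more weeks.

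*Direction and size.* The one untrained group cited, in an external trial, fell by 16.4 m over a longer period. Net change without training could therefore be negative. This stands as a reason to report the interval, not to assume its sign. A reader might also infer that most of the expected gain is practice; the documents give no figure for that.

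*It is a pilot with other safeguards.* The Background leaves randomised comparison to later trials, and a dose-response analysis is planned. However, the Background also aims to identify changes after the intervention, and the statistical section sets a significance threshold. In a dose-response regression, a shift common to all patients goes into the intercept and stays in the mean change.

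**Conclusion.** The concern holds in a limited form. Three walks are scheduled, two are used, and one has no role. With baseline as the clinic walk, the single-arm primary change includes whatever happens before supervised training. Under assumed positive shifts of 5, 10 or 20 m, the chance of a significant result with no programme effect rises from 5% to about 10%, 26% or 75%. Those figures rest on 46 complete pairs, an SD of 50.2 m taken from an external trial, and a paired t test. They show sensitivity and do not estimate the bias, whose size and sign the documents do not give. Separating the intervals would show short-term change outside the programme; it would not measure learning, nor would it turn the first-to-last change into a controlled training effect. The plan should be changed on this point, because the reanalysis affects what a single-arm study can conclude.

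**What to change.** In the Primary outcomes and statistical analysis sections:

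1. State which walk is baseline for 6MWT distance and calculated peak oxygen uptake, and whether the first-session walk precedes that session's exercise.
2. Fit one mixed model to all three walks with visit as a factor. Report the clinic-to-first-session and first-to-last-session changes, each with a 95% CI and the number of patients with the walks recorded.
3. Use first-to-last change as the primary, or as the key sensitivity, estimate of change over the training period. Record which of the two it is before the walks are analysed.
4. State that the early interval reflects short-term change outside the programme, not learning alone, and that first-to-last change may still contain some learning.

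The cost is a little more analysis on measurements already scheduled. The data are retrospective, so a practice walk cannot be added, and some records may lack the middle walk. The reported gain may be smaller.

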## *Outcome measures*

### **Primary outcomes**

The primary outcome is the changes in the 6MWT distance and the calculated peak oxygen uptake ( $VO_{2peak}$ ) between baseline and upon completion of prehabilitation program. A dose-response effect on 6MWT distance and calculated  $VO_{2peak}$  with regards to the number of prehabilitation sessions attended will be investigated. The 6MWT evaluates the ability of an individual to maintain a moderate level of physical endurance. Moderate to strong correlations have been found between the 6MWT and  $VO_{2peak}$  obtained with other modes of exercise testing. Participants are instructed to walk back and forth a 30m stretch of hallway for 6min at a pace that would make them tired by the end of the walk. A change in 6MWT distance of 20m was considered meaningful as this is the estimated measurement error in community-dwelling elderly. We will also assess the feasibility of the program by examining the recruitment, attrition and adherence of patients to the prehabilitation sessions. The reasons for drop-out from prehabilitation will be recorded.

### **Secondary outcomes**

Secondary outcome measures include patient reported outcomes before and after the prehabilitation program. These include the followings:

#### Emotional resilience

The Chinese (Hong Kong) version of the Depression Anxiety Stress Scale (DASS-21) will be used as a measure of psychological stress. It is widely used in the measurement of depression, anxiety and stress. This self-reported questionnaire has three subscales corresponding to depression, anxiety and stress. Each of the three subscales includes 7 items. Patients are asked to rate each item on a 4-point scale (0 to 3) based on their experience during the past week. The scores on DASS-21 are multiplied by 2 to calculate the final subscale scores, producing a maximum of 42 points in each subscale. The higher the score, the greater the severity of depression, anxiety and stress. DASS-21 will be measured at baseline and upon completion of prehabilitation.

### Nutritional outcomes

Nutritional status before and after prehabilitation will be measured using body weight, BMI, muscle mass and percentage body fat. Dietary assessment will be performed using 3-day food record. Patients will be asked to record all foods and beverages consumed over a period of 3 days. The dietary intake adequacy relative to the expected individual requirement, the energy intake, and the amount of protein intake measured from the 3-day food record will be compared before and after prehabilitation.

### Clinical outcomes

The length of hospital stay, in-hospital pulmonary complications, 30-day mortality and discharge destination (home, hospital or nursing aged-care facility) will be recorded. Pulmonary complications are defined using the NSQIP Definitions of Postoperative Complications (pneumonia, unplanned intubations, pulmonary embolism, failure to wean from the ventilator for more than 48 hours postoperatively)

### Others

Other secondary outcome measures include the changes in hand-grip strength, time-up-and-go test and 30 second sit-stand test before and after prehabilitation.

### *Sample size and statistical analysis*

According to a randomized controlled trial published 2014 that addressed the effect of prehabilitation in patients undergoing colorectal resection for cancer, the patients in prehabilitation group had their 6MWT distance significantly improved by 25.2m (SD 50.2) compared to baseline after 4 weeks exercise training, while those in control group declined by 16.4m (SD 46.0). Using a sample size calculator, a sample size of 46 will achieve 80% power to reject the null hypothesis with an effect size of 0.86 and a significant level of 0.05 using a 2-sided two-sample equal variance t-test.

Data will be analyzed using SPSS 26.0 software (SPSS, Inc, Chicago, IL, USA). Continuous variables will be presented as mean +/- standard deviation or median +/- interquartile range if not normally distributed. The Shapiro-Wilk test will be used to check data for normality. Categorical data will be shown as numbers and percentages. Comparison of continuous data will be performed with Student's *t* test with normal distribution and by Mann-Whitney U test for non-normally distributed data. Chi-square test will be used to compare groups with categorical variables. P value less than 0.05 is considered significant.

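### The 46 patients and 80% power rest on a two-sample t-test at effect size 0.86, which a single-arm study cannot run; restate them for the within-patient change and name paired tests

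*Combined protocol and SAP*

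**What the plan says.** Under Trial design the protocol states: "This is a single centered, unblinded, single-arm retrospective study". Under Primary outcomes: "The primary outcome is the changes in the 6MWT distance and the calculated peak oxygen uptake", measured between baseline and completion of the program. The same section says "A change in 6MWT distance of 20m was considered meaningful", on the ground that 20 m is the estimated measurement error in community-dwelling elderly people.

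The section Sample size and statistical analysis takes its inputs from a published randomized trial in colorectal cancer surgery. The prehabilitation arm "significantly improved by 25.2m (SD 50.2) compared to baseline after 4 weeks exercise training", and the control arm declined by 16.4 m (SD 46.0). It concludes that "a sample size of 46 will achieve 80% power to reject the null hypothesis with an effect size of 0.86", at a 0.05 significance level "using a 2-sided two-sample equal variance t-test".

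For the analysis, the same section names Student's t test for normally distributed continuous data, comparison "by Mann-Whitney U test for non-normally distributed data", and chi-square to compare groups on categorical variables. It does not say whether the t test is paired, and no comparison group is defined anywhere. Besides the primary outcome, DASS-21 (Emotional resilience), the physical-function tests (Others) and the nutritional measures are before-after comparisons. The dietary measures, for example, "will be compared before and after prehabilitation".

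**The concern.** A two-sample t-test compares two groups of different patients. This study has one group measured twice, so the stated effect size, test and power describe another design. Of the 41.6 m contrast behind the 0.86, 16.4 m (39%) is decline in a control arm that this study does not have and cannot observe. A reader therefore cannot tell from the plan what 46 patients can show about the outcome actually being analysed.

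The analysis paragraph has a related gap. Student's t test can be read as paired, but Mann-Whitney U cannot. If it were applied to before and after values when the data are not normal, it would ignore that each pair comes from one patient, and a real improvement could be missed.

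**Working it through.** **Inputs.** From Sample size and statistical analysis: change +25.2 m (SD 50.2) with prehabilitation, −16.4 m (SD 46.0) in controls, total 46, power 80%, two-sided alpha 0.05, effect size 0.86. From Primary outcomes: meaningful change 20 m. The SDs are read as SDs of the change, which is how that section presents them. The allocation ratio is not stated; 1:1 is assumed in order to reproduce 46. All power figures use the noncentral t distribution unless noted.

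**1. Reproducing the plan's figure.**
- Pooled SD = √((50.2² + 46.0²)/2) = 48.15.
- Effect size = (25.2 + 16.4)/48.15 = 41.6/48.15 = 0.864.
- Two-sample t-test at d = 0.86: 22 per arm gives 79.6%, 23 per arm gives 81.4%. So 46 = 23 + 23.
- Other readings fail: 46 per arm gives 98.3%, and a one-sample test at d = 0.86 needs only 13 patients.

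The derivation is not written out in the plan, but this is the only one of these readings that gives both 46 and about 80%.

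**2. The same source figures on the within-patient basis.** For a paired t-test the effect size is the mean change divided by the SD of the change, and the noncentrality is that effect size × √n.

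| Change (SD 50.2) | Effect size | n for 80% power | Power at n = 46 |
|---|---|---|---|
| 25.2 m | 25.2/50.2 = 0.502 | 34 (81.1%; 33 gives 79.8%) | 91.5% |
| 20 m | 20/50.2 = 0.398 | 52 | 75.3% |

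- The smallest change detectable with 80% power at n = 46 is 0.422 × 50.2 = 21.2 m.
- 95% CI half-width at n = 46: t(0.975, 45) × SD/√n = 2.014 × 50.2/√46 = 14.9 m.
- Room for missing final tests: 46 − 34 = 12 patients (12/46 = 26%) before power for 25.2 m falls below 80%.

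**3. Sensitivity to the SD of change, n = 46.** The 40 and 60 m values are an assumed range, not from the documents.

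| SD of change | Power, 20 m | Power, 25.2 m | 95% CI half-width |
|---|---|---|---|
| 40 m | 91.3% | 98.7% | 11.9 m |
| 50.2 m | 75.3% | 91.5% | 14.9 m |
| 60 m | 60.0% | 79.6% | 17.8 m |

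**4. What ignoring the pairing could cost.** This is an illustration with an assumed before-after correlation r (not in the documents), using the unpaired t-test as a stand-in for Mann-Whitney U and a normal approximation.
- With SD of change 50.2, the SD at each time point is 50.2/√(2(1 − r)).
- The unpaired test needs a mean difference of 1.987 × SD × √(2/46), while the true standard error of the mean change is 50.2/√46 = 7.40 m.
- For r = 0.5 the threshold is 1.987 × 50.2 × √(2/46) = 20.8 m. Power for 25.2 m is then P(Z > (20.8 − 25.2)/7.40) = 72%.
- The same steps give 41% at r = 0.7 and 15% at r = 0.8, against 91.5% for the paired test.

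**The case against.** The strongest reply is that the sample-size part has little practical effect. The Ethics section fixes the cohort by past clinic dates (August 2019 to November 2021), so no enrolment decision depends on it, and on the correct basis 46 is more than enough for a 25.2 m change. The Background also calls this a pilot meant to estimate feasibility and variance, for which precision is a more natural justification than power. That is fair, and it limits the weight of the point. It does not rescue the text: the plan makes a formal 80% power claim and sets a 0.05 threshold, so the claim should describe this study.

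On the tests, the statistical paragraph is generic and does not say that Mann-Whitney U will be used on before-after data. The planned dose-response analysis by sessions attended might involve comparing different patients. This too is fair: the loss of power is conditional. But almost every continuous efficacy outcome is a before-after change, and no paired non-parametric test is named.

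Finally, the 20 m figure is a measurement-error threshold and not a stated powering target, so 75.3% is information for the reader and not a failed target.

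**Conclusion.** The concern holds. The stated effect size, test and 80% power belong to a comparison of 23 prehabilitation with 23 control patients, which a single-arm study cannot make. On the within-patient basis, 46 patients with both tests give 91.5% power for 25.2 m (34 would suffice for 80%) and 75.3% for 20 m (52 would be needed for 80%), with a 95% CI half-width of 14.9 m.

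These figures assume that 50.2 m is the SD of the within-patient change and carries over from the cited trial's prehabilitation arm to this mixed surgical population, and that all 46 have both measurements. They cover 6MWT distance only; the documents give no SD for the change in calculated peak oxygen uptake, the other primary measure. The missing paired tests are the part that could alter a result. This should be fixed, but it does not undermine the study.

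**What to change.** In Sample size and statistical analysis, remove the 0.86 and the two-sample test and replace them with wording such as:

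> Assuming a mean within-patient 6MWT change of 25.2 m (SD of change 50.2 m, from the prehabilitation arm of the cited trial), 34 patients with 6MWT at both baseline and last session give 80% power at two-sided 0.05 with a paired t-test. Forty-six such patients would give 91% power and a 95% confidence interval half-width of about 15 m. For a 20 m change, 46 would give about 75% power.

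State how power and half-width move with the SD. Over an assumed 40 to 60 m, power for 20 m runs from 91% to 60% and the half-width from 12 to 18 m; label that range as an assumption. Because the cohort is already fixed by dates, giving the precision for the number of patients actually available with both tests would serve equally well. Say that the calculation covers 6MWT distance and not calculated peak oxygen uptake.

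In the analysis paragraph, name the paired t-test for all before-after comparisons (6MWT, calculated peak oxygen uptake, DASS-21, nutritional and physical-function measures), with the Wilcoxon signed-rank test when the changes are not normally distributed. Apply the normality check to the changes. Keep Mann-Whitney U only if different patients are to be compared, and then name the groups.

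The cost is rewording, with no extra patients or data. The plan will have to acknowledge that 46 patients give less than 80% power for 20 m at SD 50.2, and that the figure depends on the SD of the change.
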